Scatter plots

Scatter plots of Relative Risk versus Risk Difference presenting each type of analyzed hypoglycemia for patient experiencing at least one hypoglycemia event:

- during 24 weeks on-treatment period
- occurring at any time of the day.

2.4.5.2 Analyses of adverse events

Generalities

The primary focus of adverse event reporting will be on treatment-emergent adverse events. Pretreatment and post-treatment adverse events will be described separately.

If an adverse event date/time of onset (occurrence, worsening, or becoming serious) is incomplete, an imputation algorithm will be used to classify the adverse event as pretreatment, treatmentemergent, or post-treatment. The algorithm for imputing date/time of onset will be conservative and will classify an adverse event as treatment emergent unless there is definitive information to determine it is pretreatment or post-treatment. Details on classification of adverse events with missing or partial onset dates are provided in Section 2.5.3.

Adverse event incidence tables will present by SOC, HLGT, HLT, and PT, sorted in alphabetical order for each treatment group, the number (n) and percentage (%) of patients experiencing an adverse event. Multiple occurrences of the same event in the same patient will be counted only once in the tables within a treatment phase. The denominator for computation of percentages is the safety population within each treatment group.

Sorting within tables ensures the same presentation for the set of all adverse events within the observation period (pretreatment, treatment-emergent, and post-treatment). For that purpose, the table of all treatment-emergent adverse events presented by SOC and PT sorted by the internationally agreed SOC order and decreasing frequency of PTs within SOCs will define the

presentation order for all other tables unless otherwise specified. Sorting will be based on results for the Toujeo® treatment arm.

Analysis of all treatment-emergent adverse events

The following treatment-emergent adverse event summaries will be generated for the safety population.

- Overview of treatment-emergent adverse events, summarizing number (%) of patients with any,
 - Treatment-emergent adverse event;
 - Serious treatment-emergent adverse event;
 - Treatment-emergent adverse event leading to death;
 - Treatment-emergent adverse event leading to permanent treatment discontinuation.
- All treatment-emergent adverse event by primary SOC, HLGT, HLT, and PT, showing number (%) of patients with at least 1 treatment-emergent adverse event sorted by the SOC internationally agreed order. The other levels (HLGT, HLT, PT) will be presented in alphabetical order,
- All treatment-emergent adverse events by primary SOC and PT, showing the number (%) of patients with at least 1 treatment-emergent adverse event, sorted by the internationally agreed SOC order and by decreasing incidence of PTs within each SOC. This sorting order will be applied to all other tables, unless otherwise specified,
- All treatment-emergent adverse events (PT ≥5% in any treatment group incidence) by primary SOC and PT, showing the number (%) of patients with at least 1 treatment emergent adverse event, sorted by the internationally agreed SOC order and by decreasing incidence of PTs within each SOC,
- All common treatment-emergent adverse event (HLT incidence ≥ 2% in any treatment group) by primary SOC, HLT, and PT, showing number (%) of patients with at least 1 common treatment-emergent adverse event sorted by the SOC internationally agreed order. The other levels (HLT, PT) will be presented in alphabetical order,
- All treatment-emergent adverse events regardless of relationship and related to IMP by primary SOC, HLGT, HLT and PT, showing the number (%) of patients with at least 1 treatment-emergent adverse event, sorted by the internationally agreed SOC order. The other levels (HLGT, HLT, PT) will be presented in alphabetical order,
- All treatment-emergent adverse events by maximal severity, presented by primary SOC and PT, showing the number (%) of patients with at least 1 treatment-emergent adverse event by severity (ie, mild, moderate, or severe), sorted by the sorting order defined above.

Analysis of all treatment emergent serious adverse event(s)

• All treatment-emergent serious adverse events by primary SOC, HLGT, HLT, and PT, showing the number (%) of patients with at least 1 serious treatment-emergent adverse

event, sorted by the internationally agreed SOC order. The other levels (HLGT, HLT, PT) will be presented in alphabetical order,

• All treatment-emergent serious adverse events regardless of relationship and related to IMP, by primary SOC, HLGT, HLT, and PT, showing the number (%) of patients with at least 1 treatment-emergent serious adverse event, sorted by the internationally agreed SOC order. The other levels (HLGT, HLT, PT) will be presented in alphabetical order.

Analysis of all treatment-emergent adverse event(s) leading to treatment discontinuation

• All treatment-emergent adverse events leading to treatment discontinuation, by primary SOC, HLGT, HLT, and PT, showing the number (%) of patients sorted by the internationally agreed SOC order. The other levels (HLGT, HLT, PT) will be presented in alphabetical order.

Analysis of injection site reactions and hypersensitivity reaction TEAE(s)

• All treatment-emergent adverse events related to injection site reactions or hypersensitivity reactions, by PT, showing the number(%) of patients sorted by decreasing incidence of PTs in Toujeo®.

Analysis of adverse events of special interest

• A listing of patients with symptomatic overdose with IMP/NIMP, pregnancy and increase of ALT will be provided separately.

Analysis of pretreatment and post-treatment adverse events

- All pre-treatment adverse events by primary SOC and PT, showing the number (%) of patients with at least 1 pre-treatment adverse event, sorted by the internationally agreed SOC order and decreasing incidence of PTs in Toujeo ® within each SOC,
- All pre-treatment adverse events leading to study discontinuation by primary SOC and PT, showing the number (%) of patients, sorted by the internationally agreed SOC order and decreasing incidence of PTs Toujeo ® within each SOC,
- All post-treatment adverse events by primary SOC and PT, showing the number (%) of patients with at least 1 post-treatment adverse event, sorted by the internationally agreed SOC order and decreasing incidence of PTs Toujeo ® within each SOC,
- All post-treatment serious adverse events by primary SOC and PT, showing the number (%) of patients with at least 1 posttreatment serious adverse event, sorted by the internationally agreed SOC order and decreasing incidence of PTs Toujeo ® within each SOC,
- Listing of SAE,
- Listing of AEs leading to permanent treatment discontinuation.

2.4.5.3 Deaths

The following summaries of deaths will be generated for the safety population.

- Number (%) of patients who died by study period (on-study, on-treatment, post-study,
- Deaths in non-randomized patients or randomized but not treated patients,
- Treatment-emergent adverse events leading to death (death as an outcome on the adverse event case report form page as reported by the Investigator) by primary SOC, HLGT, HLT, and PT showing number (%) of patients sorted by internationally agreed SOC order, with HLGT, HLT, and PT presented in alphabetical order within each SOC,
- All pre-treatment adverse events leading to death by primary SOC and PT, showing the number (%) of patients, sorted by the internationally agreed SOC order and decreasing incidence of PTs within each SOC,
- All post-treatment adverse events leading to death by primary SOC and PT, showing the number (%) of patients, sorted by the internationally agreed SOC order and decreasing incidence of PTs within each SOC,
- Listing of deaths.

2.4.5.4 Analyses of laboratory variables

The summary statistics (including number, mean, median, standard deviation, minimum and maximum) of all laboratory variables (central laboratory values and changes from baseline) will be calculated for each visit or study assessment (baseline) by treatment group. This section will be organized by biological function as specified in Section 2.1.4.4.

Drug-induced liver injury

The liver function tests, namely aspartate aminotranferases (AST), alanine aminotransferases (ALT) and total bilirubin, are used to assess possible drug-induced liver toxicity at the baseline visit and will be displayed by treatment group for each parameter.

Listing of possible Hy's law cases identified by treatment group (eg, patients with any elevated ALT>3 x ULN, and associated with an increase in bilirubin $\ge 2 \times ULN$) with ALT, AST, alkaline phosphatase, total bilirubin, and the following complementary parameters: conjugated and non-conjugated bilirubin, creatine phosphokinase, serum creatinine.

Summarize the incidence of liver-related adverse events by treatment group. The number (%) of patients with events reported on the AE form for ALT increase and it is associated complementary forms will be summarized by PT.

2.4.5.5 Analyses of vital sign variables

The summary statistics (including number, mean, median, standard deviation, minimum and maximum) of all vital signs variables blood pressure, heart rate and body weight (and changes

from baseline) will be calculated for each visit or study assessment (baseline, each post baseline time point, last on-treatment) by treatment group.

The incidence of PCSAs at any time during the treatment-emergent adverse event period will be summarized by treatment group irrespective of the baseline level and/or according to the following baseline status categories:

- Normal/missing,
- Abnormal according to PCSA criterion or criteria.

The change in body weight from baseline to Week 24 will be analyzed in the safety population using a similar MMRM model as described in Section 2.4.4.1.1.

Exploratory analyses will be performed for the body weight as follow:

- Change in body weight from baseline to week 24 for patients with Randomization strata (as per IRT): SU or Meglitinides = Yes,
- Change in body weight from baseline to week 24 for patients with Randomization strata (as per IRT): SU or Meglitinides = No.

using a similar MMRM model as described in Section 2.4.4.1.1. Randomization strata: SU or Meglinitides at screening will be removed from the model.

2.4.5.6 Analyses of electrocardiogram variables

Description at baseline only for ECG according to the following baseline status categories:

- Normal/missing,
- Abnormal, not clinically significant,
- Abnormal, clinically significant.

2.5 DATA HANDLING CONVENTIONS

2.5.1 General conventions

The following formulas will be used for computation of parameters.

Reference day

The reference day for the calculation of extent of exposure, time to onset and relative days is the day of the first administration of IMP, denoted as Day 1.

Demographic formulas

Body Mass Index $(kg/m^2) = (Weight in kg)/(Height in meters)^2$.

Disease characteristics formulas

Duration of diabetes (years) = (Date of informed consent – date of diagnosis of diabetes +1)/365.25.

Age at onset of diabetes (years) = (Date of diagnosis of diabetes – date of birth +1) /365.25.

Duration of previous non-insulin anti-hyperglycemic treatment (years) = (Date of informed consent - date of first dose of previous non-insulin anti-hyperglycemic treatment +1) /365.25.

HbA1c transformation

To transform HbA1c in % to mmol/mol, the following formula is used:

IFCC = (10.93 * NGSP) - 23.50

NGSP (National Glycohemoglobin Standardization Program network) corresponds to HbA1c (%) and IFCC (International Federation of Clinical Chemistry network) to HbA1c (mmol/mol)

FPG and SMPG conversion From mg/dL to mmol/L: x 0.0555 From mmol/L to mg/dL: x 18.0148

Renal function formulas

No derivation because gender is not reported on e-CRF, so only central lab has this information.

Rate of hypoglycemia event per patient-year

Computed as [sum of number of episodes of hypoglycemia for all patients] / [sum of patient-year of exposure for all patients] with patient-year of exposure calculated per patient as number of days of exposure divided by 365.25.

Rate of hypoglycemia event per patient-year per study period:

- For ≤12 weeks: [sum of the number of episodes of hypoglycemia for all patients during the first 12 weeks] / [sum of patient-year of exposure for all patients during ≤12 weeks], with the patient-year of exposure during ≤12 weeks calculated as the number of days exposed during ≤12 weeks divided by (12x7),
- For >12 weeks to ≤24 weeks: [sum of the number of episodes of hypoglycemia since week 12 until week 24] / [sum of patient-year of exposure for all patients since week 12 until week 24], with the patient-year of exposure since week 12 until week 24 calculated as the number of days exposed since week 12 until week 24 (included) divided by (12x7),
- During 24 weeks: [sum of the number of episodes of hypoglycemia for all patients during 24 weeks of treatment period] / [sum of patient-year of exposure for all patients during 24 weeks of treatment period divided by (24x7).

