# 9.2.2 Safety endpoints

The safety endpoints are assessed by:

• Hypoglycemia events

Property of the Sanofi Group - strictly confidential

Hypoglycemia will be classified as below category and analyzed using the following variables:

- Percentage of patients with at least one episode of confirmed hypoglycemia\* and event rate during 24 weeks treatment periods,
- Rate of hypoglycemia per month computed as: 365.25/12 x (number of episodes of hypoglycemia)/(number of days exposed in time window),
- Percentage of patients and event rate of hypoglycemia by study period (for ≤12 weeks, for >12 weeks to ≤24 weeks) to evaluate the potentially increased risk of hypoglycemia during the initial 12-week after starting treatment with basal insulin,
- The diurnal distribution of the occurrence of each episode of confirmed hypoglycemia by category will be presented by two-hour timeframe over 24 hours during the 24 weeks treatment period.
- \* Note: Confirmed hypoglycemia: Any hypoglycemia confirmed by plasma glucose below the cut off value (70 or 54 mg/dL). The cut-off value of 70 mg/dL (3.9 mmol/L) for defining hypoglycemia is in line with ADA hypoglycemia definition. The cut-off value of 54 mg/dL (3 mmol/L) is chosen because it represented a degree of hypoglycemia at which patients have typically neuroglycopenic symptom.
- Adverse events (AE) or serious adverse events (SAE), including local tolerability at injection site, hypersensitivity reactions, Adverse events with special interest (AESI),
- Vital signs,
- Body weight.

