- Number and rate of hypoglycemia event per patient-year will be summarized for any hypoglycemia and each hypoglycemia category (as described in Section 2.1.4.1), excluding hypoglycemia occurring after the initiation of rescue therapy,
- Number and rate of hypoglycemia event per patient-year will be summarized by study period (for ≤12 weeks, for >12 weeks to ≤24 weeks and during 24 weeks treatment period) for any hypoglycemia and each hypoglycemia category (as described in Section 2.1.4.1), except probable and pseudo). Non classified hypoglycemia will be displayed. For each hypoglycemic event, the rate ratio, and its corresponding 95% CI, of Toujeo arm over Tresiba arm will be estimated using an over-dispersed Poisson regression model adjusted on randomization strata of screening HbA1c (<8.0%, ≥8.0%) and randomization strata of SU or meglitinides at screening (Yes versus No).

For Hypoglycemic ADA categories, in addition of threshold \leq 70 mg/dL (3.9 mmol/L), hypoglycemia episodes with plasma glucose <54 mg/dL (3.0 mmol/L) will be analyzed.

For each type of Hypoglycemia: Cumulative number and rate hypoglycemia event per 100 patientdays will be summarized by time of the day. Figures will be provided.

Cumulative mean number of hypoglycemia will be summarized over time using Nelson-Aalen estimates. Figures will be provided.

In addition, to help the interpretation of the results, an exploratory analysis defined as risk difference could be performed.

Subgroups analyses

The proportion of patients with at least one:

- Severe and/or confirmed (\leq 3.9 mmol/L [\leq 70 md/dL]) hypoglycemia,
- Severe and/or confirmed (<3.0 mmol/L [<54 md/dL]) hypoglycemia.

during the 24-week on-treatment period, will also be presented by the following subgroups:

- Age group (<65 and \geq 65 years of age),
- Gender (male, female),
- Baseline BMI (<30; [30 − 35[; ≥35 kg/m²),
- Randomization stratum of screening HbA1c ($\leq 8.0\%$, $\geq 8.0\%$),
- Randomization stratum of SU or meglitinides at screening (Yes vs No).

- Number of previous non-insulin anti-hyperglycemic agent (0, 1, 2, >2)
- Previous non-insulin anti-hyperglycemic treatment at screening, GLP-1RA (yes/no),
- Previous non-insulin anti-hyperglycemic treatment at screening: DPP-4 inhibitor (yes/no),
- Previous non-insulin anti-hyperglycemic treatment at screening: SGLT-2 inhibitor (yes/no),
- Duration of diabetes ($<10, \ge 10$ years),

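### The SAP labels hypoglycemia rates by study period as per patient-year but divides exposure days by 84 or 168 instead of 365.25

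*SAP*

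**What the plan says.** SAP 2.5.1 (General conventions) gives two sets of formulas for the hypoglycemia rate.

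- The general rate is total events over total patient-years, "with patient-year of exposure calculated per patient as number of days of exposure divided by 365.25".
- The next heading keeps the same unit: "Rate of hypoglycemia event per patient-year per study period". Under it, the first-period bullet ends "with the patient-year of exposure during ≤12 weeks calculated as the number of days exposed during ≤12 weeks divided by (12x7".
- For the second period, exposure is "calculated as the number of days exposed since week 12 until week 24 (included) divided by (12x7".
- For the full period, the denominator is the "sum of patient-year of exposure for all patients during 24 weeks of treatment period divided by (24x7". The square bracket that opens this denominator is never closed, and the bullet does not mention days.

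These formulas feed planned tables. SAP 2.4.5.1 states: "Number and rate of hypoglycemia event per patient-year will be summarized by study period". It names the first 12 weeks, the second 12 weeks and the 24 weeks together. The same section separately plans an overall rate per patient-year.

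The protocol gives no support for a different year. Section 11.4.3.2.1 expresses event rates per patient-year of exposure. Section 9.2.2 defines a monthly rate on the calendar scale: "Rate of hypoglycemia per month computed as: 365.25/12 x (number of episodes of hypoglycemia)/(number of days exposed in time window". SAP 1.5, which lists departures from the protocol's statistical section, mentions no change to rate units.

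**The concern.** A patient-year cannot last 84 days in one bullet, 168 days in another and 365.25 days in the definition just above them. The smaller divisor inflates the exposure denominator, so each period rate comes out too low for its label.

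The absolute frequency of hypoglycemia is at stake. A reader who takes the label at face value would conclude that hypoglycemia was much rarer than it was, and could not compare the period rates with other trials. The same 24 weeks would also carry two different rates, both called per patient-year, from the same SAP section. The protocol splits the study at week 12 to look for a higher risk during early treatment, so these tables are likely to be read closely.

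**Working it through.** **Inputs.** All divisors come from SAP 2.5.1: 365.25 days (general rate), 12x7 = 84 days (each 12-week period) and 24x7 = 168 (24 weeks). The documents contain no event counts, so the event rates below are assumed for illustration.

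**Step 1: formula.** Let E be events, D exposure days and c the divisor.

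Rate = E / (D/c) = E x c / D

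For the same events and days, the ratio of the true annual rate to the SAP period rate is therefore 365.25/c.

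**Step 2: size of the error.** The last row reads the 24-week bullet as days divided by 168, in parallel with the two bullets above it.

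| Period | c | True rate / SAP rate | Patient-years credited for full exposure | True patient-years | Rate too low by |
|---|---|---|---|---|---|
| Up to 12 weeks | 84 | 365.25/84 = 4.348 | 84/84 = 1.000 | 84/365.25 = 0.230 | 1 - 0.230 = 77% |
| 12 to 24 weeks | 84 | 4.348 | 1.000 | 0.230 | 77% |
| 24 weeks | 168 | 365.25/168 = 2.174 | 168/168 = 1.000 | 168/365.25 = 0.460 | 1 - 0.460 = 54% |

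**Step 3: what the table would show.** Assume a constant true rate of 6 events per patient-year.

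- Each 12-week period: 6 x 84/365.25 = 1.38
- 24 weeks: 6 x 168/365.25 = 2.76
- General formula: 6.0

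A second illustration assumes 460 patients in an arm, all fully exposed, with one event per patient per 12 weeks.

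- Each 12-week period as written: 460 / (460 x 84/84) = 1.00
- 24 weeks as written: 920 / (460 x 168/168) = 2.00
- With 365.25, both periods: 460 x 365.25 / (460 x 84) = 920 x 365.25 / (460 x 168) = 4.348

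**Step 4: internal check.** A correct 24-week rate is the exposure-weighted mean of the two 12-week rates, so it must lie between them. As written it is 168/84 = 2 times that mean. With full exposure in both halves it equals the sum of the two rows, as the 1.00 and 2.00 above show.

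**Step 5: literal reading of the 24-week bullet.** If the patient-years are already in units of 365.25 days and are then divided by 168, the rate is 168 times too high. In the second illustration it is 4.348 x 168 = 730.5. Neither reading gives a rate per patient-year.

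**Step 6: comparison between arms.** The model is stated as follows: "Tresiba arm will be estimated using an over-dispersed Poisson regression model adjusted on randomization strata of screening HbA1c". If exposure enters as log(D/c) = log D - log c, the constant goes into the intercept and the treatment coefficient does not move. A check with assumed counts (300 events in 38,000 days against 350 in 38,200) gives a crude rate ratio of 0.862 with divisor 84 and 0.862 with 365.25.

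**The case against.** The strongest reply is that nothing inferential changes. The primary analysis, the percentages of patients with events, the odds ratios, the relative risks and the rate ratios with their confidence intervals do not depend on this constant. The overall rate has its own correct formula. SAP 2.4.5 calls the safety analysis essentially descriptive. The two 12-week rates share the divisor 84, so the contrast between early and later treatment also survives. Protocol section 4 describes the comparison between the two insulins as of particular interest, and that comparison is intact. All of this stands, and it limits the damage to absolute rates, their label, and comparison with the 24-week row, the overall rate and other trials.

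The second point is that 2.17 is less certain than 4.35, because the 24-week bullet is incomplete. That is fair. Dividing days by 168 is the natural parallel with the two bullets above, but it is an inference.

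Third, the protocol formula in section 9.2.2 is a rate per month. It shows a consistent calendar scale across time windows but does not itself define a patient-year. Section 11.4.3.2.1 is the better source for the unit.

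One could also argue that rates per 12 or per 24 weeks were intended. No text says so, and the per-patient-year label appears both in the formula heading and in the analysis section. If that was the intention, the label is the error and still has to change.

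**Conclusion.** The concern holds. As written, SAP 2.5.1 would produce rates labelled per patient-year that are too low by a factor of 4.35 in each 12-week period. For the 24 weeks the factor is 2.17, on the reading that days are divided by 168. The 24-week rate would conflict with the SAP's own overall rate for the same period and would not lie on the scale of the two 12-week rows.

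The factors rest only on the stated divisors. The example rates of 6 and 4.348 per patient-year are illustrative, and the documents hold no results, so the conclusion concerns what would be reported if the formulas were programmed literally. Comparisons between arms within a period, and between the two 12-week periods, are not affected.

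**What to change.** In SAP 2.5.1, define patient-years in all three period bullets as the days exposed in that period divided by 365.25, summed over patients. Rewrite the 24-week bullet so that its bracket closes and it names days as the input. It should then give the same value as the general formula over the same on-treatment window, which is a useful programming check.

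If rates per 12 or per 24 weeks are really wanted, keep the divisors, rename the rates accordingly in SAP 2.5.1 and 2.4.5.1 and in the table titles, and do not call them per patient-year.

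The cost is a short SAP correction and one constant in the program. No data collection or model changes. It should be made before the tables are programmed.
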